4.2.7 Patient's Choice of Treatment for the Treatment Continuation Period

The number and proportion of patients who select each treatment administration route for the Treatment Continuation Period will be summarized on the FAS. Results will be displayed by randomized treatment sequence and overall. The proportion of responses will be based on the number of patients who started the treatment continuation period.

A consistency table with answer to question 1 of the PPQ will also be provided by randomized treatment sequence and overall. For each patient's preference category as per the question 1 of the PPQ (SC, IV and No preference), the number and percentage of patients who select each treatment administration route for the Treatment Continuation Period (SC, IV) will be summarized. The percentage of patients will be based on the number of patients who answered both PPQ question 1 and patient's choice of treatment for the treatment continuation period.

4.2.8 EORTC QLQ-C30

EORTC data will be analyzed based on the FAS, unless specified otherwise.

Summary statistics (mean, standard deviation, median, and range) of linearly transformed absolute scores and mean changes from baseline will be calculated for all

items and subscales (treatment-related symptoms and function, Global Health Status/HRQoL) of the EORTC QLQ-C30 at each assessment timepoint for each randomized treatment arm.

The EORTC QLQ-C30 data will be scored according to the EORTC scoring manual (Fayers et al. 2001). Missing data will be reported by timepoint. In the event of incomplete data, for all questionnaire subscales, if more than 50% of the constituent items are completed, a pro-rated score will be computed consistent with the scoring manuals and published validation reports. For subscales with less than 50% of the items completed, the subscale will be considered as missing. PRO completion, compliance rates, and reasons for missing data will be summarized at each timepoint by randomized treatment arm on the FAS.

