3.3.4 Rationale for Randomized Cross-Over Design

The primary objective of this study is to assess participant-reported preference for atezolizumab SC compared with atezolizumab IV. Participants will be randomized to receive either atezolizumab SC for three treatment cycles followed by atezolizumab IV for three treatment cycles versus receiving atezolizumab IV first, followed by atezolizumab SC. Participants in both treatment groups will then choose either IV or SC administered atezolizumab for their remaining treatment cycles.

Randomization accommodates potential treatment sequencing-related differences such as in the nature and/or frequency of infusion-related reactions (IRRs) with either administration route (e.g., if IRRs to IV formulation occur more frequently in the early cycles of dosing) or in adverse events attributable to switching administration routes. At the same time, the cross-over design provides exposure to both study regimens allowing each participant to act as their own control for PROs measured after atezolizumab Cycle 3 and atezolizumab Cycle 6.

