4.3.2.1 Atezolizumab SC

Atezolizumab (1875 mg) SC injections will be administered subcutaneously by a health care professional in the anterior thigh region per the instructions outlined in Table 1.

The injection site should be alternated between the left and right thigh. New injections should be given at least 2.5 cm from the old site and never into areas where the skin is red, bruised, tender, or hard. In all cases, start and stop times of the SC injection should be captured.

No premedication will be allowed for the first dose of atezolizumab SC. Premedication may be administered for Cycles ≥ 2 at the discretion of the treating physician. Injection sites will be digitally photographed after a SC injection if a severe adverse reaction at the injection site is observed. Digital recordings will be stored at the site.

In case a participant develops unacceptable toxicity to the SC injection of atezolizumab, treatment with IV infusion may continue. In case a participant develops toxicity that is linked to the treatment with atezolizumab irrespective of the form of administration (SC or IV), further continuation of treatment is not recommended. Refer to Appendix 9 for further guidance on atezolizumab toxicity management.

Administration of atezolizumab SC will be performed in a monitored setting where there is immediate access to trained personnel and adequate equipment and medicine to manage potentially serious reactions. For anaphylaxis precautions, see Appendix 8. Atezolizumab SC injections will be administered per the instructions outlined in Table 1.

Table 1 Administration of First and Subsequent Atezolizumab SC Injections

First and Subsequent SC Injections

 • No premedication is permitted prior to the first SC injection. • For subsequent SC injections, if the participant experienced an injection-related reaction with any previous injection, premedication with antihistamines, antipyretics, and/or analgesics may be administered at the discretion of the investigator. • Vital signs should be measured as described in Section 4.5.4. • Participants should be informed about the possibility of delayed post-injection symptoms and instructed to contact their study physician if they develop such symptoms

PK=pharmacokinetic.

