4.5.8.2 Description of Clinical Outcome Assessment Instruments *Patient Preference Questionnaire*

The PPQ is a generic preference questionnaire designed to ask patients about which route of administration they preferred after receiving both the SC and IV formulations. Question 1 asks patients to report their preference for the route of administration (IV, SC, or no preference). Question 2 asks patients to rate the strength of their preference (if any) on a 3-point scale (very strong, fairly strong, not very strong). Question 3 asks patients to provide two main reasons for their preference (see [Appendix 4](#)).

The PPQ will be completed immediately after 3 cycles of each treatment (i.e., Day 1 of Cycle 6 of the Treatment Crossover Period) to allow participants to have experience with both routes of administration and to determine if additional treatment by one route or another modified their preference. Please refer to [Appendix 1](#) for instructions regarding when participants who prematurely discontinue study treatment should complete the PPQ.

Therapy Administration Satisfaction Questionnaires

Participant-reported treatment satisfaction with atezolizumab IV and atezolizumab SC will be evaluated using the TASQ-IV and TASQ-SC, respectively (see [Appendix 4](#)).

Each TASQ will be completed by the participant as outlined in the schedule of activities (see [Appendix 1](#)).

EORTC QLQ-C30

The QLQ-C30 is a validated, reliable self-report measure (Aaronson et al. 1993; Fitzsimmons et al. 1999) (see [Appendix 4](#)). It consists of 30 questions that assess five aspects of participant functioning (physical, emotional, role, cognitive, and social), three symptom scales (fatigue, nausea and vomiting, and pain), global health status and quality of life (QoL), and six single items (dyspnea, insomnia, appetite loss, constipation, diarrhea, and financial difficulties) with a recall period of the previous week. Scale scores can be obtained for the multi-item scales. The functioning and symptoms items are scored on a four-point scale that ranges from "not at all" to "very much", and the global health status and QoL items are scored on a seven-point scale that ranges from "very poor" to "excellent". The QLQ-C30 takes approximately 10 minutes to complete. The QLQ-C30 will be completed by the participant as outlined in the schedule of activities (see [Appendix 1](#)).

Healthcare Professional Questionnaires

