6.5 SECONDARY ENDPOINT ANALYSES

Participant assessed satisfaction with atezolizumab SC and atezolizumab IV will be based on participant responses to Question 1 of the TASQ-SC and TASQ-IV respectively. In addition, responses of the TASQ-SC and TASQ-IV will be summarized by domain (physical impact, psychological impact, impact on activities of daily living, convenience and satisfaction).

The proportion of participants who select each treatment administration route for the Treatment Continuation Period will be summarized for all participants who complete the Treatment Cross-over Period.

EORTC QLQ-C30 scores including change from baseline, will be summarized by treatment arm and by time.

Healthcare professional perception of time/resource use and convenience with atezolizumab SC will be assessed by summarizing responses to individual questions of the HCPQs.

The percentage of participants with continuing clinical benefit after 16 cycles of atezolizumab will be summarized (stratified by disease stage at study entry).

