- x Participants in Arm A will complete the Therapy Administration Satisfaction Questionnaire for SC administration (TASQ-SC) immediately following study treatment administration on Day 1 of Cycle 3 of the Treatment Cross-over Period and the Therapy Administration Satisfaction Questionnaire for IV administration (TASQ-IV) immediately following study treatment administration on Day 1 of Cycle 6 of the Treatment Cross-over Period. Participants in Arm B will complete the TASQ-IV and TASQ-SC immediately following study treatment administration on Day 1 of Cycle 3 and 6 of the Treatment Cross-over Period, respectively.
- y During the study treatment periods, participants must complete the EORTC QLQ-30 and EQ-5D-5L before the participant and clinician receives any information on disease status and prior to treatment administration on the scheduled visit day. EORTC QLQ-C30 and EQ-5D will be administered at Cycle 7, 10, 13, and 16 of the Treatment Continuation Period.
- z Each Healthcare Professional Questionnaire (HCPQ) will be completed by the applicable HCP after each study treatment preparation and/or administration for each participant. Applicable HCPs are described in each of the questionnaires (HCPQ-Treatment Room, HCPQ-Drug

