Appendix 1: Schedule of Activities

Preparation Area). Instructions for which questions should be completed in each questionnaire at each timepoint are indicated in the introduction to each questionnaire.

- ^{aa} Medication (e.g., prescription drugs, over-the-counter drugs, vaccines, herbal or homeopathic remedies, nutritional supplements) used by a participant in addition to protocol-mandated treatment from 7 days prior to initiation of study treatment until the treatment discontinuation visit.
- ^{bb} After informed consent has been obtained but prior to initiation of study treatment, only serious adverse events caused by a protocol-mandated intervention should be reported. After initiation of study treatment, all adverse events will be reported until 30 days after the final dose of study treatment or until initiation of new systemic anti-cancer therapy, whichever occurs first, and serious adverse events and adverse events of special interest will continue to be reported until 90 days after the final dose of study treatment or until initiation of new systemic anti-cancer therapy, whichever occurs first. After this period, all deaths, regardless of cause, should be reported. In addition, the Sponsor should be notified if the investigator becomes aware of any serious adverse event that is believed to be related to prior exposure to study treatment (see Section 5.6).
- ^{cc} Participants should receive their first dose of study drug on the day of randomization, if possible. If this is not possible, the first dose should occur no later than 5 days after enrollment. For administration instructions, please check the Pharmacy Manual.
- ^{dd} After Cycle 6, participants will select the route of administration (SC or IV) they would like to receive from Cycle 7 onwards.

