
 Evaluate HCP perception of time/resource use and convenience for administration with atezolizumab SC and IV 	
 HCP responses to the Healthcare Professional Questionnaires (HCPQs), by individual question

 Evaluate HRQoL with atezolizumab SC and atezolizumab IV 	
 Change in symptoms and function from baseline and over time as assessed by European Organization for Research and Treatment of Cancer Quality of Life Questionnaire C30 (EORTC QLQ-C30) scores

	
 • Mean and mean changes from baseline score in HRQoL by cycle as assessed by the Global Health Status/Quality of Life (GHS/QoL) scale (items 29 and 30) of the EORTC QLQ-C30

 • Monitor the ongoing clinical benefit of atezolizumab 	
 • Proportion of participants with continuing clinical benefit after 16 cycles of atezolizumab, as assessed by the investigator according to local standard of care
Safety Objectives	Corresponding Endpoints

 • Evaluate the overall safety and tolerability of atezolizumab SC and atezolizumab IV 	
 • Incidence, severity, and nature of adverse events, with severity determined according to National Cancer Institute (NCI) Common Terminology Criteria for Adverse Events, Version 5.0 (CTCAE v5.0) • Safety laboratory values • Vital signs • ECG

 • Evaluate the safety of switching from atezolizumab SC to atezolizumab IV and from atezolizumab IV to atezolizumab SC 	
 • Incidence, severity, and nature of adverse events, with severity determined according to NCI CTCAE v5.0 during the study Treatment Cross-over Period by treatment arm • Safety laboratory values during the study Treatment Cross-over Period by treatment arm • Vital signs during the study Treatment Cross-over Period by treatment arm • ECG during the study Treatment Cross-over Period by treatment arm
Exploratory Pharmacokinetic Objective	Corresponding Endpoint

 • Characterize the exposure of atezolizumab when given intravenously or subcutaneously 	
 • Serum atezolizumab concentration at specified timepoints during SC and IV administration
Exploratory Immunogenicity Objective	Corresponding Endpoints

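### QLQ-C30 is summarised only by randomised arm, so there is no result by route from Cycle 10 onward and no within-participant SC-minus-IV difference from the cross-over

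*SAP*

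**What the plan says.** SAP Table 2 gives the secondary objective as "Evaluate HRQoL with atezolizumab SC and atezolizumab IV". The endpoints listed against it are QLQ-C30 change from baseline over time, and mean and mean change in global health status by cycle. For the analysis, SAP 4.2.8 presents absolute scores and changes "of the EORTC QLQ-C30 at each assessment timepoint for each randomized treatment arm". Protocol 6.5 agrees: "EORTC QLQ-C30 scores including change from baseline, will be summarized by treatment arm and by time". SAP 4.1 applies the same grouping, by assigned sequence, to all PRO analyses.

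Four other statements determine what an arm summary can show:

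- **Timing.** Protocol Appendix 1 (footnote y) has QLQ-C30 completed "prior to treatment administration on the scheduled visit day". It is scheduled at Cycles 1, 3 and 6, then at Cycles 7, 10, 13 and 16, and at end of treatment.
- **Recall.** Protocol 4.5.8.2 describes the instrument "with a recall period of the previous week".
- **Route after the cross-over.** Protocol Appendix 1 (footnote dd): "After Cycle 6, participants will select the route of administration (SC or IV) they would like to receive from Cycle 7 onwards".
- **Route within the cross-over.** Protocol 4.3.2.1 allows a departure from sequence: "In case a participant develops unacceptable toxicity to the SC injection of atezolizumab, treatment with IV infusion may continue".

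Protocol 3.3.4 justifies the cross-over as "allowing each participant to act as their own control for PROs measured after atezolizumab Cycle 3 and atezolizumab Cycle 6". Protocol 3.3.5 says the HRQoL evaluation is meant to show how symptom and treatment burden differ between the two routes.

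**The concern.** The objective concerns HRQoL on SC and on IV, while the tables describe Arm A and Arm B. These coincide only while arm determines route. Once participants choose, each arm mean is a mixture of SC and IV patients and describes neither route. A reader could take two similar arm curves late in the trial as evidence that route makes no difference to HRQoL, when the comparison could not have shown one.

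During the cross-over the problem is different. Arm and visit together identify the scheduled route, but the plan stops at separate arm means. Each participant with both assessments supplies an SC score and an IV score, yet no difference between them is estimated. The main statistical advantage of a cross-over is unused for this objective.

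The SAP groups by route elsewhere. HCPQ timing questions are stratified by route (4.2.9), continuation-period exposure is split by route (4.3.1), and TASQ is route-specific because it has two versions.

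**Working it through.** **The plan's own figure.** The only sample size stated is for the preference endpoint: p = 0.70, 95% CI half-width 0.08, 28% not evaluable.

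- n = 1.96² × 0.70 × 0.30 / 0.08² = 126.05, against 126 stated.
- 126 / (1 − 0.28) = 175, as stated.

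Both reproduce. No figure is given for QLQ-C30, so 126 is used below as an assumed number of complete pairs.

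**Which assessments identify route.** Because the form is pre-dose with a one-week recall, each assessment reflects the last dose before that visit.

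| Assessment | Last scheduled dose before it | Does arm give the route? |
|---|---|---|
| Cycle 3 | Cycle 2 | Yes, as scheduled |
| Cycle 6 | Cycle 5 | Yes, as scheduled |
| Cycle 7 | Cycle 6 | Yes, as scheduled |
| Cycles 10, 13, 16 | A chosen-route dose | No |
| End of treatment | Depends on when treatment stopped | No, for those past Cycle 6 |

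Arm gives the scheduled route at 3 of 7 post-baseline assessments and not at the other 4. For participants who stop before Cycle 7, the end-of-treatment route follows from arm and the number of cycles received, but not from arm alone.

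**What the late arm means contain (illustration).** If choice followed the plan's assumed 70% SC preference among 126 completers, 0.70 × 126 ≈ 88 would be on SC and 0.30 × 126 ≈ 38 on IV, so each arm mean from Cycle 10 would be a 70/30 mix. This places everyone not preferring SC on IV, although PPQ Question 1 also allows no preference.

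Let pA and pB be the shares choosing SC and let the route effect be a constant δ. Then the arm difference is:

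(μ + pA·δ) − (μ + pB·δ) = (pA − pB)·δ

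This is 0 when uptake is equal, and 10% to 30% of δ for gaps of 0.1 to 0.3.

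**Precision available in the cross-over.** Assumptions: 126 pairs split 63/63, equal SD at both visits, within-person correlation ρ. The ρ values are not in the documents.

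- Two arms contrasted at one visit: SE = SD × √(4/126) = 0.178 SD; half-width 1.96 × 0.178 = 0.349 SD.
- Paired difference: SE = SD × √(2(1 − ρ)/126).

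| ρ | Paired SE (SD) | 95% half-width (SD) |
|---|---|---|
| 0.3 | 0.105 | 0.207 |
| 0.5 | 0.089 | 0.175 |
| 0.7 | 0.069 | 0.135 |

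**Why the two sequences should be averaged.** With period effect π (Cycle 6 relative to Cycle 3), SC minus IV has mean δ − π in Arm A (SC first) and δ + π in Arm B. The equal-weight average is δ. Pooling all pairs gives δ − π(nA − nB)/(nA + nB). With assumed completers of 70 and 56, π = 0.20 SD and δ = 0.15 SD, the bias is 0.20 × 14/126 = 0.022 SD, so pooling gives 0.128 SD. Simulation with 20,000 runs per setting agreed: 0.127 to 0.128 SD pooled and 0.149 to 0.150 SD averaged.

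**The case against.** The listed endpoints are scores and changes by visit, and SAP 4.2.8 delivers them. The protocol and SAP agree, the trial tests no hypothesis on its primary endpoint, and no SC-minus-IV contrast is listed. All of that stands. It means no listed endpoint is missing, but it does not make the tables answer an objective framed by route.

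The own-control sentence in Protocol 3.3.4 refers to PROs measured after Cycles 3 and 6. TASQ and PPQ are given after dosing and QLQ-C30 before, so that sentence may chiefly concern satisfaction and preference. This is a fair reading. The point does not depend on it, because the route-based objective in SAP Table 2 and the rationale in Protocol 3.3.5 are specific to HRQoL.

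At Cycles 3, 6 and 7 a reader can map arm to scheduled route. This holds for participants who kept to their sequence, and an approximate mean contrast could be worked out by hand if the same participants contribute at both visits. Its SD and CI could not be recovered from arm tables.

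By-route results from Cycle 10 would be self-selected, and participants who followed the schedule will by then have had both routes. This stands: such tables cannot isolate a route effect and should accompany the arm tables, not replace them.

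Finally, a pre-dose form with one-week recall in a 21-day cycle omits the administration itself, so the true difference may be small. That is plausible, and TASQ covers administration burden. A small difference is still better reported with an interval than left unestimated.

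**Conclusion.** The concern holds. At 4 of the 7 post-baseline QLQ-C30 assessments the planned summaries do not describe HRQoL with either route (at end of treatment, for those who continued past Cycle 6), and the cross-over yields no SC-minus-IV estimate with an interval. The count of 4 comes from the documents alone. The precision figures rest on assumptions: 126 complete pairs (the preference target, not a QLQ-C30 completion figure), equal SDs, and ρ between 0.3 and 0.7. The dilution result assumes a constant route effect. The departure from sequence allowed by Protocol 4.3.2.1 adds some mismatch between arm and route within the cross-over, which the documents do not quantify. This is a descriptive secondary objective; the primary analysis and the 126/175 sample size are unaffected. It should be corrected because a stated objective is otherwise left largely unanswered with data already being collected.

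**What to change.** Amend SAP 4.2.8 in three ways:

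1. Label each post-baseline QLQ-C30 assessment by the route of the last dose received before it, including end of treatment for participants who stop before Cycle 7.
2. Add the within-participant SC-minus-IV difference for Cycle 3 versus Cycle 6, with a 95% CI. Each of these assessments follows two scheduled doses of its route. Compute the mean difference within each sequence and average the two with equal weight, which removes the period effect. State that this assumes no differential carry-over.
3. From Cycle 10 onward, show QLQ-C30 by route received as well as by arm, marked descriptive and non-randomised.

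The same paired difference could be added for TASQ Question 1 and the domain scores. TASQ already reports each route by sequence and overall, so only the difference is absent there.

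The cost is SAP wording and a few tables, with no new data: route in the continuation period is already needed for the exposure tables in SAP 4.3.1. Two limits should be stated with the results. The late by-route summaries reflect participant choice, and the paired difference uses only participants with both the Cycle 3 and Cycle 6 assessments.

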4.2.9 Healthcare Professional Questionnaire (HCPQ)

Healthcare professional perception of time/resource use and convenience with atezolizumab SC will be assessed by summarizing responses to individual questions of the HCPQs on the FAS by randomized treatment sequence and overall.

The percentage of responses will be based on the number of respondents in the respective questionnaire. HCPQ will also be summarized by each healthcare professional specialty.

Healthcare Professional Questionnaire-Treatment Room

The number of HCPQs completed, the specialties of Healthcare Professional Respondents (Nurse, Pharmacy Technician, Oncologist, Gynaecologist) will be summarized overall.

Experience with atezolizumab SC injection and atezolizumab IV infusion administration

Responses to individual questions will be summarized by cycle and stratified by route of drug administration.

Impact on Clinical Management and Clinical Efficiency

Responses to individual questions 2 to 8 will be summarized overall.

Healthcare Professional Questionnaire-Drug Preparation Room

The number of HCPQs completed and the specialties of Healthcare Professional Respondents (Nurse, Pharmacist, Pharmacy Technician) will be summarized overall.

Experience with atezolizumab SC and atezolizumab IV infusion Dispensing and Preparation

Response to the question 1b "How long did it take to prepare the treatment for use?" will be summarized by cycle and stratified by route of drug administration (question 1a).

Impact on Clinical Management and Clinical Efficiency

Responses to individual questions 2 to 4 will be summarized overall.

